#### **6.2.13 CDR**

The CDR (Hughes, 1982) is a semi-structured interview resulting in a semi-quantitative scoring of cognitive impairment in milder and more progressed forms of dementia. The overall CDR rating, along with the memory box score, will be used to determine a subject's eligibility for inclusion. The CDR score - SB will also be used in calculating treatment group means for change from baseline calculation. Standardized CDR will be conducted by the Investigator or designee.

CDR score (sum of boxes) is the sum of each domain score.

#### **6.2.14 MMSE**

The MMSE (Folstein et al, 1975) consists of 11 tests of orientation, memory (recent and immediate), concentration, language, and praxis. Scores range from 0 to 30, with lower scores indicating greater cognitive impairment. It is based on the performance of the subject and takes approximately 5 to 10 minutes to administer. Standardized MMSE (Version 2.0) will be conducted by the Investigator or designee. The MMSE score is used for eligibility as well as calculating treatment group means for change from baseline.

#### **6.2.15 Columbia-Suicide Severity Rating Scale (C-SSRS)**

The C-SSRS is a clinician-administered instrument that assesses suicidal ideation and behavior (38TPosner, 201138T).

The following outcomes are C-SSRS categories and have binary responses (yes/no). The categories have been re-ordered from the actual scale to facilitate the definition of composite endpoints:

Category 1	Wish to be Dead
Category 2	Non-specific Active Suicidal Thoughts
Category 3	Active Suicidal Ideation with Any Methods (Not Plan) without Intent to Act
Category 4	Active Suicidal Ideation with Some Intent to Act, without Specific Plan
Category 5	Active Suicidal Ideation with Specific Plan and Intent
Category 6	Preparatory Acts or Behavior
Category 7	Aborted Attempt
Category 8	Interrupted Attempt
Category 9	Actual Attempt (non fatal)
Category 10	Completed Suicide

Suicidal Ideation since baseline – A “yes” answer at any time during double blind treatment to any one of the 5 suicidal ideation questions (categories 1-5) on the C-SSRS.

Suicidal Behavior since baseline – A “yes” answer at any time during double blind treatment to any one of the 5 suicidal behavior questions (categories 6-10) on the C-SSRS.

There will be no imputation of missing data for C-SSRS.

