4.2. Exclusion Criteria

Subjects meeting any of the following criteria are not eligible for enrollment in this study:

1. Evidence that the primary basis for cognitive impairment is neurodegenerative disease other than AD, including, but not limited to, vascular dementia, dementia with Lewy bodies, and Parkinson’s disease.
2. Suicidality, defined as active suicidal thoughts within 6 months before Screening or at Baseline, defined as answering yes to items 4 or 5 on the Columbia-Suicide Severity Rating Scale (C-SSRS), or history of suicide attempt in previous 2 years, or, in the Investigator’s opinion, at serious risk of suicide.
3. History of major and active psychiatric disorder, moderate to severe depressive symptoms, and or other concurrent medical condition that, in the opinion of the Investigator, might compromise safety and/or compliance with study requirements.
4. Diagnosis of alcohol or drug abuse within the previous 2 years.

5. History of cancer within the last 5 years, except basal cell carcinoma, squamous skin carcinoma, prostate cancer or carcinoma in situ with no significant progression over the past 2 years.
6. Poorly controlled clinically significant medical illness, such as hypertension (blood pressure >180 mmHg systolic or 100 mmHg diastolic); myocardial infarction within 6 months; uncompensated congestive heart failure or other significant cardiovascular, pulmonary, renal, liver, infectious disease, immune disorder, or metabolic/endocrine disorders or other disease that would preclude treatment with p38 mitogen activated protein (MAP) kinase inhibitor and/or assessment of drug safety and efficacy.
7. History of serum B12 abnormality, anemia with hemoglobin ≤ 10 g/dL, thyroid function abnormality, electrolyte abnormality, or positive syphilis serology that have not been corrected and/or otherwise addressed.
8. History of epilepsy or unexplained seizure within the past 5 years.
9. Aspartate aminotransferase (AST) or alanine aminotransferase (ALT) $> 2.5 \times$ the upper limit of normal (ULN), total bilirubin $> 1.5 \times$ ULN, and/or International Normalized Ratio (INR) > 1.5 .
10. Known human immunodeficiency virus or active hepatitis B or hepatitis C virus infection.
11. Subject participated in a study of an investigational drug less than 3 months or 5 half-lives of the investigation drug, whichever is longer, before enrollment in this study.

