6. STUDY ASSESSMENTS AND PROCEDURES

6.1. Schedule of Assessments

The schedule of assessments is presented in [Table 6-1](#).

Table 6-1 Schedule of Assessments

Assessment	Study Period / Visit Number / Study Day									
	Screening ^a		Treatment Period						ET Visit ^c	Follow-Up Visit ^d
	1 ^a	2 ^a	3	4	5	6	7	8		
	Within 42 days of D1		1 ^b	21 (±3)	42 (±3)	84 (±5)	126 (±5)	168 (±5)	Within 3 days after last dose	14 (±3) of last dose
Informed Consent	X ^e									
Medical history review	X									
Pregnancy testing	X ^f									
Physical examination ^g	X							X	X	X
Vital signs	X	X	X	X	X	X	X	X	X	X
C-SSRS	X		X	X	X	X	X	X	X	
Prior/concomitant medication	X	X	X	X	X	X	X	X	X	X
Adverse events recording ^h	X	X	X	X	X	X	X	X	X	X
Hematology and chemistry ⁱ	X		X	X	X	X	X		X	X
Coagulation studies ⁱ	X					X				X
12-lead electrocardiogram ^j	X							X	X	
MMSE ^k	X		X			X				X
CT/MRI ^l		X								
HVLT-R and WMS ^k			X		X	X		X	X	
CDR	X					X		X	X	
Lumbar puncture ^m		X						X ⁿ	X ^{n,o}	
Dispense study drug ^p			X	X	X	X	X			
Pharmacokinetic sampling ^q				X	X	X				
CYP2C19 genotyping and optional ApoE4 testing ^r			X							
Final study drug reconciliation								X	X	

CDR: Clinical Dementia Rating Scale; C-SSRS: Columbia-Suicide Rating Scale; CT: Computed tomography; D=day; HVLT-R: Hopkins Verbal Learning Test – Revised; MMSE: Mini-Mental State Examination; MRI: Magnetic resonance imaging; WMS: Wechsler Memory Scale.

Note: Telephone contacts will be conducted to determine subject status and assess compliance between Days 42 and 84 (Visits 5 and 6); Days 84 to 126 (Visits 6 and 7); and Days 126 and 168 (Visits 7 and 8).

- a. Two Screening visits are planned to allow most screening procedures to be completed and reviewed during the first visit before lumbar puncture is performed at Visit 2. All screening assessments should be conducted within 42 days of Day 1.
- b. On Day 1, all procedures should be conducted prior to first dose of study drug.
- c. Subjects who prematurely discontinue study drug for any reason will be asked to return to the clinical site for an Early Termination visit within 3 days following the last study drug dose; if it is determined that the subject will discontinue study drug while at the study center for a scheduled visit, then the Early Termination visit should be conducted at that time.
- d. The Follow-up Visit should be conducted within 14 (± 3) days of the last dose of study drug for subjects who complete the study or discontinue early.

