6.2.2. Columbia-Suicide Severity Rating Scale

The C-SSRS is a clinician-administered instrument that assesses suicidal ideation and behavior ([Posner, 2011](#)). The “Baseline” version of the instrument will be administered to subjects during Screening, and the “Since Last Visit” version will be used at subsequent time points specified in [Table 6-1](#).

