### 6.3 Conventions

All data listings, summaries, figures and statistical analyses will be generated using SAS version 9.3 or higher.

Summaries will be presented by treatment group or overall. Treatment group labels will be displayed as follows:

Neflamapimod  
(40 mg)

Placebo

*Overall columns are to be included within the table shells as follows:*

Demography	Treatment and overall
Baseline	Treatment and overall
Disposition	Treatment and overall
Efficacy	Treatment
PD	Treatment
PK	Treatment
AEs	Treatment
Other safety	Treatment

Listings will be sorted in the following order treatment group, subject, parameter, and visit unless otherwise stated. All data will be listed, subjects who were not randomized will be displayed after the randomized treatment groups.

Continuous variables will be summarized by the number of non-missing observations, mean, median, standard deviation, and minimum and maximum. For all tabulations of changes from baseline data, the lower and upper 95% confidence limits for the mean for the individual treatments will be given.

Categorical variables will be summarized by presenting the frequency and percent. Percentages will be based on the number of non-missing observations or the subject population unless otherwise specified. For each variable, all categories will be shown. Zero frequencies (but not the percent) within a category will be presented.

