16.2.8.1.1	Hematology Results (Enrolled Subjects)	IP	

Listing Number	Listing Title	Validation Method	Shell Number (if repeat)
16.2.8.1.2	Chemistry Results (Enrolled Subjects)	IP	
16.2.8.1.3	Coagulation Results (Enrolled Subjects)	IP	
16.2.8.1.4	Clinically Significant Laboratory Results (Enrolled Subjects)	IP	
16.2.8.1.5	Laboratory Liver Function and Coagulation Parameter Abnormalities (Enrolled Subjects)	IP	
16.2.8.2	Vital Signs (Enrolled Subjects)	IP	
16.2.8.3	12-lead ECG Parameters (Enrolled Subjects)	IP	
16.2.8.4	Physical Examination, Abnormal Results (Enrolled Subjects)	IP	
16.2.8.5	Columbia Suicide Severity Rating Scale (C-SSRS) Questionnaire (Enrolled Subjects)	IP	

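### The SAP's 'since baseline' C-SSRS ideation endpoint does not separate new or worsened ideation from persisting ideation, and neither C-SSRS composite is summarised by arm

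*SAP*

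**What the plan says.** SAP 6.2.15 re-orders the C-SSRS into ten categories (1-5 ideation, 6-10 behaviour) in order to define composite endpoints, and then defines two:

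- Ideation since baseline: a yes "at any time during double blind treatment to any one of the 5 suicidal ideation questions (categories 1-5) on the C-SSRS".
- Behaviour since baseline: a yes "at any time during double blind treatment to any one of the 5 suicidal behavior questions (categories 6-10) on the C-SSRS".

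Neither definition mentions the pre-dose response.

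On the scale itself, Protocol 4.2 (exclusion 2) bars a subject for "answering yes to items 4 or 5 on the Columbia-Suicide Severity Rating Scale (C-SSRS". Exclusion 2 also covers a suicide attempt in the previous 2 years and serious risk in the Investigator's opinion.

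Table 6-1 schedules the C-SSRS at the first Screening visit, Day 1, the five later treatment visits and Early Termination. Under Protocol 6.2.2 the Baseline form is given at Screening, and the 'Since Last Visit' "version will be used at subsequent time points specified in" Table 6-1. Day 1 sits under the Treatment Period columns, but a table note says: "On Day 1, all procedures should be conducted prior to first dose of study drug".

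SAP 6.13.1 to 6.13.5 cover adverse events, laboratory data, vital signs, ECG and physical examination. In Section 11, the other-safety tables (14.3.7) are all ECG tables. The only C-SSRS output is listing 16.2.8.5, "Columbia Suicide Severity Rating Scale (C-SSRS) Questionnaire (Enrolled Subjects".

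**The concern.** The label 'since baseline' suggests a change from the subject's state at entry, but the rule records only whether any ideation was reported on treatment. A subject who enters with category 3 ideation and improves to category 1 is an event. A subject who goes from category 1 to category 5 is the same event. Any rate built from this rule would mix persisting with new ideation and would not show a shift in severity.

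The SAP applies stricter logic elsewhere. Under 6.13.1 a pre-existing adverse event is treatment-emergent only if it becomes more severe after the first dose. The C-SSRS rule does not follow that convention.

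The second part concerns output. The composites are defined and then never summarised, so the planned report would contain no by-arm C-SSRS result. If a table were requested after unblinding, the definition of an emergent event would have to be chosen with the data in view.

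**Working it through.** **1. The plan's own figure.** The only design calculation is for the primary endpoint (SAP section 4): 76 per arm, two-sided alpha 0.05. Power = Φ(ES × √(76/2) − 1.96).

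- ES 0.53: Φ(3.267 − 1.96) = 0.904, against a stated 90%.
- ES 0.46: Φ(2.836 − 1.96) = 0.809, against a stated 80%.

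Both reproduce. They bear on the C-SSRS only by fixing 76 per arm.

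**2. The two SAP rules side by side.** Apply the SAP ideation rule, and a rule built on the SAP's adverse event logic (onset or worsening), to the worst category before and after first dose:

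| Pre-dose worst | On-treatment worst | SAP 6.2.15 ideation | Onset-or-worsening logic |
|---|---|---|---|
| none | 1 | event | event |
| 3 | 3 | event | no event |
| 3 | 1 | event | no event |
| 1 | 5 | event | event |
| 2 | none | no event | no event |

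The rules differ only in rows 2 and 3, where entry ideation persists or recurs without worsening. Row 5 shows that entry ideation is not counted automatically: later visits use the 'Since Last Visit' form, so it must be reported again.

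**3. The reference point.** SAP 6.2.2 sets baseline as the last non-missing pre-dose value. For the C-SSRS that is Day 1, on a form covering only the interval since the previous visit. A subject positive at Screening and negative on Day 1 would then have no ideation at baseline. The SAP also does not say whether the Day 1 answer, taken before dosing but at a visit filed under Treatment Period, falls within double-blind treatment.

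**4. Direction of the effect (illustration only).** The documents give no C-SSRS rate, so every rate here is assumed. Let b be the share of each arm whose entry ideation persists or recurs, and p the new-onset rate in the rest. The counted rate is b + (1 − b)p. Take p = 2% on placebo and 8% on drug.

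| b | Placebo | Drug | Difference | Ratio | Power (normal) | Power (Fisher) |
|---|---|---|---|---|---|---|
| 0% | 2.0% | 8.0% | 6.0 points | 4.00 | 0.40 | 0.24 |
| 5% | 6.9% | 12.6% | 5.7 points | 1.83 | 0.22 | 0.15 |
| 10% | 11.8% | 17.2% | 5.4 points | 1.46 | 0.15 | 0.11 |

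For b = 5%: 0.05 + 0.95 × 0.02 = 0.069; 0.05 + 0.95 × 0.08 = 0.126; 0.126/0.069 = 1.83. Normal-approximation power is Φ((d − 1.96·se0)/se1), where d is the difference in rates and se0 and se1 are its pooled and unpooled standard errors, at 76 per arm.

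The absolute difference barely moves, while the ratio and the power fall. Persisting ideation dilutes the contrast.

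**5. What the sample size allows in any case.** With b = 0, 2% against 4% has power 0.11 (Fisher 0.02). Only a very large contrast is detectable with good power: 2% against 15% gives 0.83 (Fisher 0.79). With no events in 76 subjects, the one-sided 95% upper limit is 1 − 0.05^(1/76) = 3.9%.

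**The case against.** A reader might infer that the trial cannot show whether the drug raises suicidality. The documents do not support that:

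- The data are collected at every treatment visit, and SAP 6.3 orders the output: "Listings will be sorted in the following order treatment group, subject, parameter, and visit unless otherwise stated". By-arm counts and severity shifts can be taken from listing 16.2.8.5.
- SAP section 6 allows additional tables in the study report.
- Suicidality reported as an adverse event enters the by-arm treatment-emergent tables (SAP 6.13.1). Withdrawal reasons are also tabulated by arm (SAP 6.4).
- The firmer limit on inference is 76 per arm, which no definition changes.

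A reader might also infer that all entry ideation is carried into the count, or that most counted events would not be emergent. The 'Since Last Visit' form rules out the first. The second needs an entry prevalence, a persistence rate and an emergent rate, none of which the documents give. Exclusion 3 (major active psychiatric disorder, or moderate to severe depressive symptoms) plausibly lowers the first of these. Randomisation balances persisting ideation in expectation, so the comparison is diluted rather than invalid.

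Nor does the carry-over argument extend to behaviour in the same way. With the 'Since Last Visit' form, that composite counts acts reported for a later interval, and it needs no change beyond a clear starting point.

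All of this stands and narrows the point. It does not supply a by-arm C-SSRS summary or a rule separating new or worsened ideation from persisting ideation.

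**Conclusion.** The point holds in two parts. First, the ideation composite gives persisting or recurring category 1-3 ideation the same weight as new or worsened ideation, out of line with the SAP's own adverse event rule. Second, neither composite is summarised by arm anywhere in the planned analyses or output list.

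The consequence is a safety report less informative than the collected data allow. The primary analysis is unaffected, and the safety question remains answerable from the listing, within the limits of the sample size. No magnitude is claimed: the rates in the illustration are assumed and show direction only.

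The conclusion rests on Section 11 being the complete output list. I could read SAP 6.5 to 6.7 only in part, but their headings (protocol deviations, baseline comparability, medical history) do not suggest a C-SSRS summary there.

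**What to change.** In SAP 6.2.15:

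- Keep both any-on-treatment composites.
- Add treatment-emergent ideation: the highest post-dose category (1-5) is above the highest pre-dose category across Screening (Baseline form) and Day 1 ('Since Last Visit' form), with no ideation ranked below category 1.
- State that the Day 1 response is pre-dose and is not on-treatment.
- Leave the behaviour rule as any category 6-10 after first dose.

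Add a C-SSRS paragraph to SAP 6.13, and one by-arm Safety Population table to 14.3.7 giving n and % with any ideation, emergent ideation, emergent category 4-5 ideation, and behaviour. All of this should be fixed before unblinding.

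The cost is SAP wording and one more descriptive table, with no new data collection. The main drawback is that the pre-dose reference combines two forms whose recall windows may differ; the documents do not state the window of the Baseline form. If it reaches further back, an old report could raise the reference and hide a later event. Keeping the any-on-treatment composite in the same table guards against that.

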### **6.2.16 Early Termination Efficacy Assessments**

For analysis purposes, efficacy data collected from early termination (ET) visit will be assigned to the next scheduled visit.

### **6.2.17 Unscheduled Visits**

In general, only scheduled post-baseline laboratory, ECG, and vital signs values will be tabulated. Post-baseline repeat/unscheduled assessments will be disregarded from table, although these post-baseline assessments will be listed in the relevant appendices to the CSR.

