3.1.4. Early Discontinuation

Subjects who prematurely discontinue study drug for any reason will be asked to return to the clinical site for an Early Termination visit within 3 days following the last study drug dose; if it is determined that the subject will discontinue study drug while at the study center for a scheduled visit, then the Early Termination visit should be conducted at that time. These subjects will also be asked to return to the clinical site for a Follow-up Visit 14 (± 3) days following the last study drug dose.

Every effort should be made to ensure a subject returns for this visit.

Refer to [Section 4.3](#) for details regarding removal of subjects from treatment.

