### 6.2.2 Baseline and Change from Baseline

Baseline is defined as the last non-missing value (either scheduled, unscheduled or repeat) before the subject receives first dose of study drug (Day 1). Visit 3 (Day 1) date is defined as the date of the first dose.

Baseline score of MMSE for each subject is calculated using the average of Screen and Day 1 measurements.

Change from baseline  $CHG = AVAL - BASE$  where  $AVAL$  is the post-baseline value,  $BASE$  is the baseline value.

Baseline z-score will be used as a covariate in the MMRM and ANCOVA analysis. It will be calculated as below:

For baseline total recall, a z-score for each subject is defined by  $z = (x - m) / s$  where  $x$  is the subject's total recall at baseline, and  $m$  and  $s$  are the overall mean and overall standard deviation of total recall at baseline across all subjects. Similarly, a baseline z-score for each subject for delayed recall can be calculated.

A composite baseline z-score for each subject is calculated using equal weighting in the following way:

$Z = 0.5 * z\text{-score for total recall at baseline} + 0.5 * z\text{-score for delayed recall at baseline}$ .

The calculation method can be referenced to [Section 6.2.12](#).

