### **Liver Function Parameter**

The number and percentage of subjects meeting certain liver function abnormality categories will be summarized by visit:

- Alanine Aminotransferase (ALT) assessment > 3 times upper limit of normal (ULN),

- Aspartate aminotransferase (AST) > 3xULN,
- ALT or AST: > 3xULN; > 10xULN; > 20xULN
- Total Bilirubin: > 1.5xULN; > 2xULN
- Alkaline Phosphatase: > 1.5xULN; >2xULN
- (ALT or AST > 3xULN) and total bilirubin>2xULN
- (ALT or AST>3xULN) and total bilirubin>2xULN and alkaline phosphatase<2xULN

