### Coagulation Parameter Abnormalities

- International Normalized Ratio (INR) >1.5

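### Off-schedule threshold crossings can drop out of the by-arm liver, INR and QT/QTcF counts, and the SAP's treatment-related definition omits the Related category

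*SAP*

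**What the plan says.** SAP 6.2.17 sets a general rule for laboratory, ECG and vital-sign tables. Scheduled post-baseline values are tabulated; for the rest, "Post-baseline repeat/unscheduled assessments will be disregarded from table", and they go to listings. The rule opens with a general qualifier but names no exception.

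The threshold counts are defined later:

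- SAP 6.13.2, liver: "The number and percentage of subjects meeting certain liver function abnormality categories will be summarized by visit". The categories include ("ALT or AST > 3xULN) and total bilirubin>2xULN".
- SAP 6.13.2, coagulation: "International Normalized Ratio (INR) >1.5", with nothing further.
- SAP 6.13.4, ECG: counts by group and visit of subjects whose maximum QT or QTcF, or maximum increase from baseline, falls in given bands.

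None of these mentions unscheduled values. Before dosing, SAP 6.2.2 does admit them: baseline is the "last non-missing value (either scheduled, unscheduled or repeat") value before first dose.

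For early termination (ET), SAP 6.2.16 says that "efficacy data collected from early termination (ET) visit will be assigned to the next scheduled visit". No matching sentence for laboratory or ECG data appears in the SAP text available.

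On causality, protocol 7.1.5 has three levels: Not related, Possibly related and Related. SAP 6.13.1 names the middle level alone as treatment-related, then counts a missing relationship as related.

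**The concern.** A threshold count answers whether a subject ever crossed a limit after starting treatment. Repeat and unscheduled tests are often done because something looked abnormal, so they are a natural place for a crossing to appear. A rule that removes them suits by-visit means but can undercount crossings.

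Tables 14.3.4.7 and 14.3.7.4 are where the arms are compared on these limits. Few crossings are expected: protocol 3.2.1.2 reports no liver-test abnormalities in either Phase 2a study. The same section does report transaminase increases in 10% to 15% of rheumatoid arthritis patients, at a higher dose and at plasma concentrations 4- to 5-fold higher. With counts this small, one missing subject can change what a row shows.

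The causality definition raises a separate question. It feeds Tables 14.3.1.4 and 14.3.1.7 and Listing 14.3.2.3. Read literally, the events most firmly attributed to the drug leave those outputs while events with no attribution stay in, and the outputs could disagree with Table 14.3.1.4.1, which shows causality.

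**Working it through.** The plan states no figure to reproduce on this point. The check compares the tabulation rule with what the schedule collects.

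**1. Scheduled post-baseline tests.** From protocol Table 6-1, as read from the PDF text (cell positions should be confirmed against the PDF):

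| | D21 | D42 | D84 | D126 | D168 | ET | Follow-up |
|---|---|---|---|---|---|---|---|
| Chemistry | X | X | X | X | – | X | X |
| "Coagulation studies" (INR) | – | – | X | – | – | – | X |
| 12-lead ECG | – | – | – | – | X | X | – |

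- Chemistry columns: 6. INR columns: 2. Chemistry columns without a scheduled INR: 6 − 2 = 4 (D21, D42, D126, ET).
- If the blank Day 168 chemistry cell is a PDF reading loss, the figures become 7 columns, 2 with INR and 7 − 2 = 5 without.
- ECG: Day 168 for completers or ET for others, so 1 per subject.

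**2. Consequence for INR.** Protocol 4.3 names two laboratory combinations with ALT or AST >3x ULN: total bilirubin >2x ULN, and INR >1.5. SAP 6.13.2 has a row for the first and none for the second, so 1 of 2. If transaminases are raised at Day 21, 42, 126 or ET, an accompanying INR can only be off schedule, and SAP 6.2.17 keeps it out of the table. Subjects who stop early "will be asked to return to the clinical site for an Early Termination visit within 3 days following the last study drug dose", but that visit has no scheduled INR. Unless stopping coincides with Day 84, the first scheduled INR after stopping is at Follow-up: 14 − 3 = 11 to 14 + 3 = 17 days after the last dose.

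**3. Consequence for QT/QTcF.** With one scheduled post-baseline ECG per subject, and several readings at one visit averaged (SAP 6.2.10), a scheduled-only maximum is a single value. The maximum rows carry extra information only if off-schedule ECGs count. An increase from baseline may start from an unscheduled ECG (SAP 6.2.2) but may not end at one (SAP 6.2.17).

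**4. Weight of one subject.** 1/76 = 1.3%.

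**5. Illustration with assumed rates.** The documents give neither the crossing rate p nor the fraction f of crossing subjects seen only off schedule. With 76 subjects in an arm, the chance that a row shows zero is (1 − p(1 − f))^76:

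| p | f = 0 | f = 0.25 | f = 0.50 |
|---|---|---|---|
| 2% | 21.5% | 31.7% | 46.6% |
| 5% | 2.0% | 5.5% | 14.6% |
| 10% | <0.1% | 0.3% | 2.0% |

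The effect is largest where crossings are rare. These values show sensitivity and do not estimate a loss.

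**6. Causality.** The protocol levels that imply attribution are Possibly related and Related. The SAP definition names the first; its next sentence adds missing. Related is not named.

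**The case against.** The strongest reply is that nothing is lost and the protocol's commitment is met. Protocol 8.6 promises listings of individual clinically significant laboratory and ECG changes, with summary statistics by group; it does not promise by-arm threshold counts. Off-schedule values stay in listings sorted by treatment group, including 16.2.8.1.4 and 16.2.8.1.5. Laboratory abnormalities that need diagnostic tests or lead to discontinuation become adverse events (protocol 7.1.4), as does clinically significant ECG worsening (protocol 6.2.10), so they reach the by-arm adverse-event tables. A subject above 3x ULN at a scheduled visit is already in that row. The general qualifier in SAP 6.2.17 leaves room for an exception, the table shells are not in the text reviewed, and SAP 6.13.4 plans box plots of maximal ECG change without saying which ECGs feed them.

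Much of this stands, and it limits the point to the threshold tables. It does not repair them. Adverse-event tables count preferred terms, not multiples of ULN or msec, and a listing is not a count. The SAP can write an any-time rule when it wants one: SAP 6.2.15 does so for the suicidality scale.

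Two side arguments carry little weight. ET is itself a scheduled column, so its chemistry and ECG values are probably tabulated even though no mapping rule was found. Using the last pre-dose value as baseline is ordinary practice. It is also fair that the protocol set the sparse INR schedule, and that a separate transaminase-with-INR row is not obligatory, since each component already has its own row.

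On causality, the sentence counting missing as related makes a drafting slip the likely explanation, and Table 14.3.1.4.1 would still show the events.

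**Conclusion.** The concern holds and is minor. Followed as written, SAP 6.2.17 lets a liver, INR or QT/QTcF crossing seen only off schedule go uncounted in Tables 14.3.4.7 and 14.3.7.4. The number of subjects affected cannot be derived; each would be 1.3 percentage points of a 76-subject arm.

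The supporting schedule figures (INR at 2 of 6 or 2 of 7 chemistry columns, one ECG per subject) depend on Table 6-1 having been read correctly, and they describe opportunity rather than loss. The conclusion also assumes that the general qualifier is not used to make an unwritten exception.

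The treatment-related definition is a separate wording fault, and the intent is probably to include Related. Neither point affects efficacy results or removes data.

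**What to change.** These are reporting changes; no stopping rule or visit schedule is altered.

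1. In Tables 14.3.4.7 and 14.3.7.4, add a per-subject worst post-baseline count by arm using all scheduled, unscheduled, ET and Follow-up values, and write this as an exception in SAP 6.2.17.
2. In Table 14.3.4.7, add a row for ALT or AST >3x ULN with INR >1.5, matching the combination named in protocol 4.3. For this row and the existing bilirubin row, say whether both values must come from the same sampling date. Rows for >5x and >8x ULN are optional.
3. State that the maximum QT/QTcF rows use all post-baseline ECGs, and whether the within-visit averaging of SAP 6.2.10 applies to them.
4. Keep by-visit means scheduled-only.
5. In SAP 6.13.1, define treatment-related as possibly related, related, or relationship missing, so that Tables 14.3.1.4 and 14.3.1.7 and Listing 14.3.2.3 agree with Table 14.3.1.4.1.

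The cost is a few sentences in the SAP and some table programming on data already collected.
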